1.0 Background & Rationale

Chronic kidney disease (CKD) is a common chronic disease, affecting approximately 26 million American adults (1). CKD-mineral bone disorder (CKD-MBD) is a condition of disordered bone and mineral metabolism that contributes to morbidity and mortality in patients with CKD (2). CKD-MBD is characterized by the presence of all or some of the following features: laboratory abnormalities related to calcium and phosphorus homeostasis, bone disease, and vascular calcification. These abnormalities begin to appear early in the disease process (3), and virtually all patients with moderate to advanced CKD exhibit some or all features of the disorder. The clinical consequences of CKD-MBD are dire and include increased cardiovascular events, bone fragility fractures, and mortality (4-7). In fact, cardiovascular events are the leading cause of death in patients with CKD (8, 9). Thus, prevention and management of CKD-MBD is of critical importance to reduce morbidity and mortality in these patients. Calcium (Ca) and phosphorus (P) homeostasis are central to CKD-MBD development. ***However, lack of understanding on Ca and P metabolism in CKD-MBD progression precludes the development of effective therapies.***

Ca and P are intimately related in physiology and metabolism(10). They share common hormonal regulators that include parathyroid hormone (PTH), 1,25-dihydroxyvitamin D (1,25D), and fibroblast growth factor 23 (FGF23) that act on a common tissue axis of intestine, kidney, bone, and parathyroid glands. Treatments aimed at managing CKD-MBD affect the hormonal and tissue axes of both ions and have diverse effects on Ca and P serum levels. For example, calcitriol lowers serum P while increasing serum Ca (11, 12); whereas calcimimetics lower serum P while also lowering serum Ca (13). More importantly, serum or plasma

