4.2 Exclusion Criteria

- Plans to initiate dialysis within 6 months
- Hypercalcemia defined as serum calcium >10.5 mg/dL within past 3 months
- Hyperkalemia defined as serum potassium >5.5 mg/dL within past 3 months
- Hyperphosphatemia defined as serum phosphate >5.5 mg/dL within past 3 months
- Intestinal disease that alters absorption or normal intestinal function including celiac disease, small bowel resection, or bariatric surgery
- Serious, *uncontrolled* underlying systemic disease including diabetes, lupus, hypertension (as deemed by the PI).
- Pregnant or breastfeeding
- Taking a phosphate binder medication, calcitriol, vitamin D analogs, calcimimetics, PTH analogues, and other medications that may alter Ca and P metabolism within past 30 days
- Vegan or vegetarian diet, lactose intolerance and/or milk allergy

Figure 1. Current CKD Nomenclature Used by KDIGO Guidelines

[figure not shown]
Green: low risk (if no other markers of kidney disease, no CKD); Yellow: moderately increased risk; Orange: high risk; Red, very high risk.

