6.0 Enrollment/Randomization

We aim to study N = 4 subjects, although seek approval enrolling up to 6 subjects due to the small sample size of 4 and the need for high adherence. Based on study diet and urine and fecal collection adherence of >90%, N = 2 patients that meet this level of adherence will be asked to continue with the full balance and kinetics protocol (Aim 2) on a first-enrolled basis. Thus 2 subjects will complete the absorption study (Aim 1), and 2 subjects will complete the full balance and kinetic studies (Aim 1 and Aim 2). It will be determined before a subject signs consent which consent they will sign (Consent A = Aim 1 or consent B= Aim 1 and Aim 2).

Recruitment will target moderate stage CKD patients aged 30-75 years old. Subjects will be recruited from patients seen in CKD clinics of the IU/Eskanazi Nephrology group who are partners of the co-investigators.

- Personnel from the IUSM Division of Nephrology will review medical charts from nephrology clinics for pre-screening to determine potential eligibility. An email will be sent to the doctors of the identified potential subjects to obtain their permission for enrollment and the potential subjects will be contacted by phone or visited by study staff during clinic.
- Information about the study may be discussed with interested potential subjects by research personnel by phone, email or in person as preferred by the subject/clinic.
- If interested, potential subjects will be either 1) scheduled for a screening visit at the Indiana Clinical Research Center, or 2) have screening information collected at the time of recruitment if subject is recruited in person at a CKD clinic by study staff.
- Prior to screening, subjects will be asked to provide written informed consent, and will be given the opportunity to have their questions about participation answered.
- Following the screening visit, all data will be evaluated by the study staff to determine eligibility of the subject. If eligible, participants will be enrolled in the study, and study visit dates will be scheduled.

Randomization Plan

At the beginning of the study, the study biostatistician will generate a randomization list for dietary intervention crossover order A or B by pairs. These orders will be A=LCa/HP to LCa/LP and B=LCa/LP to LCa/HP. Especially due to the small sample size, attention will be made to ensuring a balance of the two orders, which will be accomplished by randomizing both in pairs.

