7.0 Study Procedures

All study procedures will be conducted for the purpose of research.

Screening Visit

Following informed consent, a screening visit of approximately 60 minutes to assess eligibility will include a medical history, renal panel, and urine albumin/creatinine ratio (UACR). Recent lab values from the medical chart within ~3 months may be used if available. eGFR will be calculated from serum creatinine using the CKD-EPI equation (20). A urine pregnancy test of human gonadotropin will be performed for subjects of childbearing potential.

Pre-Study Washout Period and Run-In Period

Otherwise eligible subjects who take drugs that potentially alter calcium and phosphate balance or homeostasis including high dose cholecalciferol or ergocalciferol (1000 U/day or 50,000 U/wk, respectively), active vitamin D metabolites, calcimimetics, PTH analogues in the last 30 days, will undergo a 30-day pre-study washout from these drugs to be eligible for the study, with their physician approval.

All subjects will be given 600 IU/d of an oral vitamin D supplement (cholecalciferol) for 2-weeks prior to beginning the controlled feeding period and through completion of the study. This is to ensure vitamin D intake adequacy prior to the study, as was done for our previous balance study in CKD patients(14). 600 IU/d is the current recommended dietary allowance from the Institute of Medicine (18).

Dietary Interventions

The cross-over will consist of a randomly assigned order of two dietary conditions:

1) Low Ca (500 mg/d)/high P (1500 mg/d) diet (LCa/HP)

The LCa/HP diet is at levels within the range observed for a typical American diet poor in Ca and high in P (18-21)

2) Low Ca (500 mg/d)/low P (800 mg/d) diet (LCa/LP)

The LCa/LP diet represents coupling a typical poor Ca intake with the commonly prescribed dietary P restriction of 800 mg/d (22).

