A baseline outpatient visit of approximately 60 minutes will occur on "Day 1" of the study. This is when the controlled research diet will begin. Subjects will arrive to this appointment fasting at least 8 hours and will have blood and urine collected for baseline biochemistries. These will include a renal panel, serum 25D, and urine Ca, P, creatinine, and additional serum collected for additional measures such as baseline bone and mineral biochemistries and uremic retention solutes. eGFR will be calculated from serum creatinine using the CKD-EPI equation (17). Subjects will receive 3 days of meal pack-outs and will return on the 3rd or 4th day for the remaining meals until the inpatient stay. We will obtain meal adherence data over the outpatient period using meal checklists, PEG capsule pill counts, and leftover food weigh-backs. Anthropometrics (weight, and height) and vital signs will be taken at the baseline visit. Subjects will also be asked to bring a stool collection from home to the Day 1 visit, the stool sample should be collected within 3 days prior to the visit. Stool collection supplies will be given to the subjects at the screening visit.

Ca, P, Mg Absorption Tests (Aim 1)

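### Patients who enter through the 30-day drug washout can be judged against the calcium and phosphate limits on pre-washout values; recheck before releasing study meals (minor, low-cost safety improvement)

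*Combined protocol and SAP*

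**What the plan says.** Section 4.2 excludes on two serum limits that matter here: "Hyperphosphatemia defined as serum phosphate >5.5 mg/dL within past 3 months" and "Hypercalcemia defined as serum calcium >10.5 mg/dL within past 3 months". Neither says from which date the three months are counted back.

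Section 6.0 places the eligibility decision after screening: "Following the screening visit, all data will be evaluated by the study staff to determine eligibility of the subject". Patients found eligible are then enrolled and given visit dates. Section 7.0 lists a history, a renal panel and a urine albumin/creatinine ratio at screening, and adds: "Recent lab values from the medical chart within ~3 months may be used if available".

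The same section then takes patients who are eligible apart from a listed drug (high-dose vitamin D, active vitamin D metabolites, calcimimetics, PTH analogues). They "will undergo a 30-day pre-study washout from these drugs to be eligible for the study, with their physician approval". A two-week vitamin D run-in also precedes feeding. The washout and run-in text lists no calcium or phosphate test.

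The next panel listed is on Day 1, under Baseline Measures. It is described as baseline chemistry, with no threshold or action attached. Of Day 1 the protocol says: "This is when the controlled research diet will begin". Three days of packed meals are given out at that visit, and the rest are collected on day 3 or 4.

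**The concern.** The washout moves the patient from an on-drug to an off-drug state, and the trial studies the off-drug state. If the safety limits are applied only to on-drug values, they describe a condition the patient is no longer in when feeding begins.

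The protocol itself gives the reason to expect a difference. Section 1.0 states that "calcitriol lowers serum P while increasing serum Ca", and that calcimimetics reduce both. A patient whose phosphate passes while on either drug, or whose calcium passes while on a calcimimetic, may not pass off it. Such a patient could leave the Day 1 visit with study meals, possibly those of the 1500 mg/d phosphorus diet, before anyone is required to look at an off-drug value. What is at stake is patient safety and correct application of the sponsor's own exclusions.

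**Working it through.** The protocol states no figure to reproduce on this point. The check is of sequence, direction of drug effect, and dates.

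**1. Sequence (sections 6.0 and 7.0).** Screening labs, or chart labs up to about 3 months old → eligibility decision → 30-day washout for those eligible apart from the drug → Day 1 panel, diet start and meal release. The text between the second and last steps lists no calcium or phosphate test. The staff-initiated withdrawal rule in section 11.0 concerns diet adherence below 90%; it includes no laboratory rule.

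**2. Direction of error, by drug (section 1.0 against the section 4.2 limits).**

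| Drug stopped | Phosphate >5.5 mg/dL | Calcium >10.5 mg/dL |
|---|---|---|
| Calcitriol | On-drug value is lower, so a pass may not hold off drug | On-drug value is higher, so the check is conservative |
| Calcimimetic | On-drug value is lower, so a pass may not hold off drug | On-drug value is lower, so a pass may not hold off drug |
| High-dose vitamin D, PTH analogue | No direction given; no claim | No direction given; no claim |

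**3. Age of the qualifying value on Day 1.** Assume that the washout starts at screening and that 3 months is 90 days.
- Fresh screening draw: 0 + 30 = 30 days, or 30 + 14 = 44 days if the two-week run-in follows the washout rather than overlapping it.
- Chart value at the limit: 90 + 30 = 120 days, or 90 + 30 + 14 = 134 days.
- If the look-back is instead counted from Day 1, values older than 90 days fall outside it. Even then, the first 90 − 30 = 60 days of the window precede a washout that ends on Day 1, and no test is listed in the remaining 30 days before Day 1.

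**4. What is handed out before a Day 1 result need be seen.** High-phosphorus diet: 3 × 1500 = 4,500 mg phosphorus (4,050 to 4,950 mg at the ±10% that section 7.0 allows). Low-phosphorus diet: 3 × 800 = 2,400 mg. These are total intakes. The patient's usual intake is not stated, so they are not amounts added to it. The later meals are collected on day 3 or 4, when a Day 1 result could already be acted on.

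**5. Number affected.** The protocol does not say how many of the planned 4 patients (at most 6 enrolled) would come through the washout. It may be none.

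**The case against.** The strongest reply is that the schedule itself has not been seen. Section 8.0 only points to Appendix B, and neither that calendar nor the monitoring plan in Appendix C was in the text supplied. A reader might infer that the trial has no post-washout check at all. The documents do not support that, because either appendix could contain one. What stands is that section 7.0 does not state it.

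Second, the order is partly inferred. The washout is a condition of eligibility, so the section 6.0 decision could be read as staying open until the washout ends. The three-month look-back could also be read to include a Day 1 value. Serum 25D, an inclusion criterion, is first named among the Day 1 tests, which suggests that Day 1 results may count for eligibility. These readings are fair. None of them makes anyone read the Day 1 result before the meals leave the clinic.

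Third, a reader might extend the point to every washout drug and both limits. Section 1.0 supports it only for the cells marked in the table. It gives direction without size, and two of the studies cited for these drug effects are, by title, in dialysis patients, whereas this trial enrols patients with eGFR 30-44.

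Fourth, a reader might infer that the meals do harm or that the diet comparison is biased. Neither is shown. The protocol describes the high-phosphorus diet as within typical American intake, and any off-drug rise would come from stopping the drug, which needs physician approval. The comparison is made within patients. Physician approval and the safety board reduce the risk, but the text supplied describes neither as a calcium or phosphate limit applied before feeding.

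**Conclusion.** The point holds as a minor patient-safety and eligibility improvement. Followed as written, the text allows a washout patient who is over a section 4.2 limit off drug to start the diet. It applies to the phosphate limit after calcitriol or a calcimimetic, and to the calcium limit after a calcimimetic only.

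Its size cannot be given as a probability: the documents state neither the number of washout patients nor the size of the off-drug shift. What can be bounded is the age of the qualifying value (30 to 44 days after a fresh draw, up to about 120 to 134 days with a chart value if the look-back is counted from screening) and the food released before a result must be seen (three days of meals). No stated sample size, power or variance figure changes.

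The conclusion rests on three assumptions: that screening values precede the washout, that the renal panel includes calcium and phosphate (its components are not listed, although section 3.2 measures both in serum at all time points collected), and that Appendices B and C do not already contain the rule.

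**What to change.** Add one sentence to the washout paragraph of section 7.0: for patients who enter through the 30-day washout, serum calcium and phosphate are measured after it ends, and the existing exclusions (calcium >10.5 mg/dL, phosphate >5.5 mg/dL) are applied to that value before any study meals are released. If an appendix already says this, repeat it in section 7.0.

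There are two ways to do it:
- **Hold the packed meals until the Day 1 result has been reviewed.** This needs no new assay and no extra blood. The cost is a short delay between the draw and the start of the diet.
- **Move the Day 1 panel a few days earlier.** If the other Day 1 samples stay where they are, this adds one 7 mL draw: 7/348 = 2.0% of the section 10.0 total for Aim 1 only, or 7/432 = 1.6% of the total for Aim 2.

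The downside of either is an occasional late screen failure, which would occur before any study diet or isotope is given. Patients who do not need the washout are unaffected.

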8.0 Study Calendar

See Appendix B. "Study Calendar of Assessments"

9.0 Reportable Events

Collection of AEs will begin at the time of consent.

Prompt reportable AEs are assessed by the principal investigator (PI) as *(1) unexpected, (2) related or possibly related to study participation, AND (3) suggests that the research places subject(s) or others at greater risk of harm than was previously known.*

These will be submitted to the IRB within 5 business days of the investigators becoming aware of the event.

SAEs are any severe SE including any event leading to hospitalization, life-threatening condition, disability or incapacitation, death, or other significant hazard.

These will be reported to the IRB within 48 hours of the investigators becoming aware of the event, and in writing within 5 business days.

AEs not requiring prompt reporting will be those that are not SAEs as described above, are anticipated (i.e. described in the consent form), and do not occur any more frequently or with greater severity than expected.

These will be recorded and reported to the IRB at continuing review.

10.0 Data Safety Monitoring

The Data and Safety Monitoring Plan includes establishment of a DSMB. Members of the DSMB will include experts experienced in clinical research and patients with CKD and will consist of a Chairperson and one additional member. Please see details in the DSMP attachment.

Potential Risks

Risk of Phlebotomy and IV infusion:

The potential risks of phlebotomy are slight, but some possible risks include: excessive bleeding, fainting or feeling lightheaded, bruising, and infection (which is a slight risk any time the skin is broken). During each of the absorption test days, approximately 80 mL (11 time points of 7 mL each, approximately 5 tablespoons) of blood will be drawn over 24 hours. For comparison, the average whole blood donation is 1 pint, or 473 mL (about 32 tablespoons). Therefore, the total amount of blood drawn over the course of this study for subjects studied only under Aim 1 (absorption tests only) is 348 mL (174 mL in each crossover period (screening visit [7 mL], baseline visit [7 mL], plus the absorption test protocol [\sim 160 mL, 22 time points of 7 mL each] which will be over \sim 48 hours, which is less than that drawn in a single blood donation. For subjects in Aim 2 (full balance and kinetics), they will have an additional 42 mL (6 time points of 7 mL each) drawn over the 12 days (5 days additional inpatient and final blood draw on Day 21 outpatient) after the 48-hour absorption testing period in each session, totaling approximately 432 mL drawn over the entire study (approximately 2 months). This is a cumulative volume of blood from sequential draws of 7 mL each, to yield approximately 3 mL of serum at each time point, which is needed for analysis of P-33, Ca-44, Mg-25, Mg-26 and other biochemistries of mineral metabolism.

The Ca-44, P-33 and Mg-25 will be administered by IV in a sterile saline “push” infusion of 1-3 mL. Potential risks are rare, but could include infection at the infusion site, sepsis, or air embolism. Steps to minimize these risks are below.

Risk of Radiation Exposure:

The risk of radiation exposure from P-33 (10 μ Ci in each oral and IV dose = 40 μ Ci total over the course of the study, effective dose of 35.6 mrem) is present for this study but is similar to some other common exposures. For example, the average radiation dose from a single round-trip cross-country flight in a commercial airplane across the United States is 4 mrem, from a single chest x-ray is 8 mrem, and from a single mammogram is 30 mrem (SC Dept of Health). People in the United States receive an average of 620 mrem of radiation per year from natural and man-made radiation sources (Source: Purdue REM website; NCRP Report #160).

Ca-44 Mg-25, and Mg-26 are stable isotopes so does not carry radioactivity risk.

Risk of Diet Intervention:

The controlled LCa/HP diet is based on a typical US diet that is low in Ca and is high in P due to its ubiquity in foods (37, 38). The LCa/LP diet changes the dietary P content to the level recommended when dietary P restrictions are prescribed. Thus, the controlled LCa/HP diet is at a level that would not be atypical in average, healthy American, and the LCa/LP diet reflects what would be commonly consumed by a CKD patient on a P restricted diet. Diets will be designed to meet the estimated energy needs of each subject to maintain current weight.

Potential risks of the controlled diet are feelings of hunger or being overly full on the research diet. A potential risk for food borne illness is present as is the case with any food consumption.

For patients with diabetes, there is risk of potential hypoglycemia with the study diet due to potential differences in amount and pattern of food consumed on study compared with at home.

Risk of Loss of Confidentiality:

As with all research studies, there is a risk of loss of confidentiality. Steps to minimize this risk are described in the following section.

Protections against Risks**Risk of Phlebotomy and IV Infusions:**

To minimize risk from venipuncture and IV infusions, only trained personnel on the Indiana CTSI CRC will draw blood, place IVs, and push the IV infusions, using sterile supplies and technique. The IV infusion will be Ca-44, P-33, and Mg-25 in sterile saline. A sterile procedure for preparing these doses has been approved by the Indiana University Radioactive Drug Research Committee (RDRC) that we have used in prior studies. We send dose samples for each batch made to an independent certified lab for sterility and endotoxin testing.

Risk of Radiation Exposure:

Oral and IV doses of P-33 will be analyzed by liquid scintillation to confirm the appropriate radiation activity is given to subjects. The closest amount to 10 uCi that can be accurately measured without going over the limit of 11 uCi per dose will be given and recorded (e.g. 1.4356 mL may be needed for exactly 10 uCi, so 1.4 mL will be accurately measured, administered, and recorded). The radiotracer tests will be performed at the Indiana Clinical Research Center under medical supervision. The protocol will be approved by the Indiana University Radionuclide Radiation Safety Committee (RRSC) and the Radioactive Drug Research Committee (RDRC). These committees have approved similar P-33 use in our prior human studies.

Risk of Diet Intervention:

If a subject reports hunger or being overly full on the research diet, the diet will be modified accordingly. Research kitchen staff are trained in safe food handling, and subjects will be given explicit instructions on how to keep their pack-out meals safe to consume (including refrigeration and reheating instruction).

For diabetic subjects, we will collect usual home diet information (4-day food record), and the study physicians and dietitian will adjust the study diet and diabetes medications accordingly for the study. Diabetic subjects will be asked to perform fingersticks at home for blood glucose monitoring, and report to the study coordinator any blood sugar < 100 mg/dL. The study coordinator will alert the MD.

The study physician orders will be amended to include a specific order to the MD (first [name], then [name]) for any BS < 100 mg/dL.

Risk of Loss of Confidentiality:

See **14.0 Privacy/Confidentiality Issues** below

